16.3. Monitoring of the Study

No site may initiate the 1-day assessments until Biogen or its designee representatives have concluded protocol-specific training and approved assessment technician(s).

Biogen or its designee representatives may conduct on-site visits at the study facilities for the purpose of monitoring various aspects of the study. The Investigator must agree to Sponsor-authorized personnel having direct access to subject (or associated) source files for the purpose of verifying entries made in the CRF and assist with their activities, if requested. Adequate space and time for monitoring visits should be made available by the Investigator or study staff. The site must complete the CRFs in a timely manner and on an ongoing basis to allow regular review by the study team.

During these visits, CRFs and supporting documentation related to the study will be reviewed and any discrepancies or omissions will be resolved.

Monitoring visits must be conducted according to the applicable ICH and GCP guidelines to ensure protocol adherence, quality of data, compliance with regulatory requirements, and continued adequacy of the investigational site and its facilities.

16.4. Study Funding

Biogen is the Sponsor of the study and is funding the study. All financial details are provided in the separate contracts between the institution, Investigator, and Biogen.

16.5. Publications

Details are included in the clinical study agreement for this study.

CONFIDENTIAL

The information contained herein may not be used, disclosed, or published without the written consent of
Biogen MA Inc.

17. FURTHER REQUIREMENTS AND GENERAL INFORMATION

17.1. External Contract Organizations

Biogen will be responsible for all administrative aspects of this study, including but not limited to, study initiation, monitoring, management of SAEs, and data management.

17.1.1. Contract Research Organization

██████████, a contract research organization (CRO), will be responsible for administrative aspects of the study, including but not limited to, study initiation, monitoring, and management of SAE reports and data management. Before subjects are enrolled at each study site, the CRO will review study responsibilities with the Investigators and other study site staff, as appropriate.

17.1.2. Electronic Data Capture

Subject information will be captured and managed by study sites on CRFs via an appropriate Web-based electronic remote data capture tool.

17.1.3. Central Facility for Other Assessments

A central facility has been selected by Biogen to be a central reader for ██████████, FF-VEP, and ██████████ for this study. A separate central facility has been selected by Biogen to read and interpret all MRI results for this study.

17.2. Changes to Final Study Protocol

All protocol amendments must be submitted to the ethics committee and regulatory authorities if required by local law. Protocol modifications that affect subject safety, the scope of the investigation, or the scientific quality of the study must be approved by the ethics committee before implementation of such modifications to the conduct of the study. If required by local law, such modifications must also be approved by the appropriate regulatory agency prior to implementation.

However, Biogen may, at any time, amend this protocol to eliminate an apparent immediate hazard to a subject. In this case, the appropriate regulatory authorities will be notified subsequent to the modification.

In the event of a protocol modification, the ICF may require similar modifications (see Section 15).

CONFIDENTIAL

The information contained herein may not be used, disclosed, or published without the written consent of Biogen MA Inc.

17.3. Ethics Committee Notification of Study Completion or Termination

Where required, the regulatory authorities and ethics committees must be notified of completion or termination of this study, and sent a copy of the study synopsis in accordance with necessary timelines.

17.4. Retention of Study Data

The minimum retention time for study records will meet the strictest standard applicable to that site, as dictated by any institutional requirements or local laws or regulations. Prior to proceeding with destruction of records, the Investigator must notify Biogen in writing and receive written authorization from Biogen to destroy study records. In addition, the Investigator must notify Biogen of any changes in the archival arrangements including but not limited to archival at an offsite facility or transfer of ownership if the Investigator leaves the site.

17.5. Study Report Signatory

Biogen will designate one of the participating Study Investigators as a signatory for the study report. This determination will be made by several factors, including but not limited to, the Investigator's experience and reputation in the studied indication; the Investigator's contribution to the study in terms of design, management, and/or subject enrollment; or by other factors determined to be relevant by Biogen.

Biogen will follow all applicable local regulations pertaining to study report signatories.

CONFIDENTIAL

The information contained herein may not be used, disclosed, or published without the written consent of
Biogen MA Inc.

# 1 STUDY OBJECTIVES AND ENDPOINTS

## 1.1 Primary Objective and Endpoint

The primary objective of this study is to assess FF-VEP latency in subjects who were enrolled in Study 215ON201 2 years (+ 4 months) after the last study visit.

[figure not shown]
The primary endpoint that is related to this objective is the change in FF-VEP latency of the affected eye as compared to the baseline of the fellow eye at 2 years (+ 4 months) after the last study visit assessment (Week 32) in Study 215ON201.

## 1.2 Secondary Objectives and Endpoints

The secondary objective is to assess clinical progression and severity of central nervous system (CNS) demyelinating disease in subjects who were enrolled in Study 215ON201 2 years (+ 4 months) after the last study visit.

The endpoints that relate to this objective are as follows:

- Evaluate incidence of clinically definite multiple sclerosis (CDMS) and time to diagnosis of CDMS.
- Evaluate severity of CNS demyelinating disease with Expanded Disability Status Scale (EDSS), Symbol-Digit Modalities Test (SDMT), and multiple sclerosis functional composite (MSFC). The MSFC includes the following:
  - Timed 25-Foot Walk (T25FW)
  - 9-Hole Peg Test (9HPT) [dominant and nondominant hands]
  - (3-Second) Paced Auditory Serial Addition Test (PASAT)
- Evaluate change in disease activity from baseline with brain magnetic resonance imaging (MRI) with and without gadolinium (Gd). MRI analysis will include the following:
  - Number of Gd-enhanced lesions
  - Volume of T2 lesions

## **2 STUDY DESIGN**

### **2.1 Study Overview**

This international multicenter, follow-up study will determine the long-term electrophysiologic and clinical outcomes in subjects previously enrolled in Study 215ON201.

One group is planned, with eligible subjects (previously enrolled in Study 215ON201) having already been administered at least 1 study treatment (BIIB033 100 mg/kg or placebo) by IV infusion once every 4 weeks for 20 weeks (a total of 6 doses). Dosing was completed 2 years (+ 4 months) prior to enrollment in this follow-up study. A maximum of 82 subjects (determined from the number of subjects who received at least 1 dose of BIIB033 or placebo in Study 215ON201) will be included in this study. There is no formal sample size calculation. The number of subjects eligible for this study is determined by the number of subjects who participated in Study 215ON201.

[figure not shown]
See Figure 1 for a schematic of the study design.

Study Duration:

The study period will consist of an approximately 1-day visit (with a +5-day window of the 1-day visit) that is dependent on the scanner capabilities and equipment availability at each clinical site.

**2.2 Study Schematic**

**Figure 1: Study Design**

IP = investigational product; MRI= magnetic resonance imaging.

Note: All assessments should be performed on the same day where possible or within a + 5 day window of the 1-day visit.

**Table 1: Schedule of Activities**

Tests and Assessments 	Day 1  (2 Years + 4 Months After Week 32 Visit in Study 215ON201 or Projected Week 32 Visit if the Subject Did Not Complete All Visits)
Informed Consent	X
Eligibility Criteria Check	X
Medical History 	X
Multiple Sclerosis Diagnosis	X
Multiple Sclerosis Signs and Symptoms	X
Concomitant Therapy and Procedures Recording	X
Vital Signs 	X
Physical Examination	X
Expanded Disability Status Scale 	X
Symbol-Digit Modalities Test	X
Multiple Sclerosis Functional Composite Including 
 
• Timed 25-Foot Walk
 
• 9-Hole Peg Test (Dominant and Nondominant Hands)
 
• (3-Second) Paced Auditory Serial Addition Test
 
	X
Full-Field Visual Evoked Potential 	X

Tests and Assessments 	Day 1 : (2 Years + 4 Months After Week 32 Visit in Study 215ON201 or Projected Week 32 Visit if the Subject Did Not Complete All Visits) 
[REDACTED]	
[REDACTED]	
Adverse Event/Serious Adverse Event Recording 	X

[REDACTED]; MRI = magnetic resonance imaging.

 All assessments should be performed on the same day and in the order listed, when possible (or within a + 5-day window of the 1-day visit).

 Completion of the Day 1 visit assessments constitutes the end-of-study visit.

 Medical history will be taken from after last study visit in Study 215ON201.

 Vital signs include temperature, systolic and diastolic blood pressure, pulse rate, body weight, and respiratory rate (after sitting for at least 5 minutes).

 Expanded Disability Status Scale should be performed by a study certified rater. Where applicable, refer to study manual for instructions.

[REDACTED]

 Sites and technicians must be qualified and approved by the central reader to perform MRI, [REDACTED], full-field visual evoked potential, and [REDACTED].

[REDACTED]

 Adverse event/serious adverse event monitoring will be recorded after informed consent form sign-off through the end-of-study visit.

### 3 STATISTICAL ANALYSIS METHODS

#### 3.1 General Considerations

Descriptive summary statistics will be presented for all study primary, secondary and [REDACTED] endpoints collected.

Unless stated otherwise, summary statistics will be presented by original treatment groups and overall. For continuous endpoints, the summary statistics will generally include number of subjects enrolled, number of subjects evaluated, mean, standard deviation, median, and range (minimum, maximum). For categorical endpoints, the summary statistics will generally include number of subjects enrolled, number of subjects evaluated, and the percent of subjects in each category.

Statistical testing for efficacy endpoints will be made between the BIIB033 group and the placebo group. There will be no multiple comparison adjustments.

Unless stated otherwise, all statistical tests will be 2-sided with statistical significance level of 0.05.

The statistical software, SAS®, will be used for all summaries and statistical analyses.

#### Analysis population

Intent-to-treat (ITT) population, per-protocol population, and safety population are defined as follows.

- *Intent-to-Treat Population*

The intent-to-treat population is defined as all randomized subjects who received at least 1 dose of study treatment (BIIB033 or placebo) in 215ON201 study, and completed at least one of the 1-day assessments in this study.

- *Per-protocol Population*

The per-protocol population is defined as subjects from the ITT population who completed the 215ON201 study, did not miss more than one dose of BIIB033 or placebo, and did not receive MS modifying therapies during study 215ON201. These subjects were included in the per-protocol population of 215ON201 study.

- *Safety population*

The safety population is defined as all subjects who received at least 1 dose of study treatment in 215ON201 and completed at least one of the 1-day assessments in this study.

#### Baseline data

Unless stated otherwise, baseline data are defined as the data collected prior to the time and/or on the date of first dose in 215ON201. If there are more than one value on or before

the date of first dose, the non-missing value closest to and prior to (including on) the date of first dose will be used as the baseline value.

### Treatment group

No study drug dosing is planned for this follow-up study. The treatment group used in the descriptive summary and treatment comparison is determined by the prior treatment with the investigational drug in 215ON201.

- new in 215ON203
  - baseline T2 volume in 215ON201 (0 and >0)
  - EDSS total score ( $\geq$ median and < median)
  - EDSS FS visual score ( $\geq$ median and < median)
  - RGCL thinning in the affected eye by week 4 ( $\geq$ median and < median)

## **3.2 Study Subjects**

### **3.2.1 Analysis population**

Unless stated otherwise, all study subjects data will be summarized by treatment groups and overall in the ITT population.

### **3.2.2 Accounting of Subjects**

The summary of subjects disposition will include: subjects who completed the study; and subjects who withdrew from study early and the reasons for withdrawal. A listing of those subjects who withdrew from study and the associated reasons for withdrawal will be presented by treatment group. Number of subjects in each analysis population defined in Section 3.1 will also be summarized.

### **3.2.3 Protocol Deviations**

Protocol deviations identified during site monitoring will be captured in a Protocol Deviation log and categorized as major or minor deviations by Biogen. Count and percentage of subjects with at least one major deviation will be summarized by category.

### **3.2.4 Demographics and Baseline Disease Characteristics**

Demographic data, including age (in years), age category (in years; <18, 18-30, 31-40, 41-50, and 51-55, >55), sex and race category, will be summarized using descriptive statistics. Demographic data will be also summarized in per-protocol population.

Medical history between last study visit Study 215ON201 and Day 1 is categorized into pre-specified system organ categories. Number and percent of subjects for each category will be summarized.

### **3.2.5 Concomitant Medications and Non-drug Treatments**

All concomitant medications will be coded using the World Health Organization (WHO) medication dictionary. A concomitant medication is any drug or substance administered between the time the subject has signed the ICF and the End of Study. A concomitant non-drug treatment is any therapeutic interventions or diagnostic assessment performed between the time the subject has signed the ICF and the End of Study.

The number and percent of subjects taking concomitant medication and non-drug treatments will be summarized by treatment group and overall.

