4.2. Schedule of Activities

Table 1: Schedule of Activities

Tests and Assessments ¹	Day 1 ² : (2 Years + up to 12 Months After Week 32 Visit in Study 215ON201 or Projected Week 32 Visit if the Subject Did Not Complete All Visits)
Informed Consent	X
Eligibility Criteria Check	X
Medical History ³	X
Multiple Sclerosis Diagnosis	X
Multiple Sclerosis Signs and Symptoms	X
Concomitant Therapy and Procedures Recording	X
Vital Signs ⁴	X
Physical Examination	X
Expanded Disability Status Scale ⁵	X
Symbol-Digit Modalities Test	X
Multiple Sclerosis Functional Composite Including 
 • Timed 25-Foot Walk • 9-Hole Peg Test (Dominant and Nondominant Hands) • (3-Second) Paced Auditory Serial Addition Test 	X

CONFIDENTIAL

The information contained herein may not be used, disclosed, or published without the written consent of Biogen MA Inc.

Tests and Assessments ¹	Day 1 ² : (2 Years + up to 12 Months After Week 32 Visit in Study 215ON201 or Projected Week 32 Visit if the Subject Did Not Complete All Visits)
[REDACTED]	[REDACTED]
Full-Field Visual Evoked Potential ⁷	X
[REDACTED]	[REDACTED]
Adverse Event/Serious Adverse Event Recording ¹²	X

[REDACTED] MRI = magnetic resonance imaging.

¹ All assessments should be performed on the same day and in the order listed, when possible (or within a +5-day window of the 1-day visit).

² Completion of the Day 1 visit assessments constitutes the end-of-study visit.

³ Medical history will be taken from after last study visit in Study 215ON201.

⁴ Vital signs include temperature, systolic and diastolic blood pressure, pulse rate, body weight, and respiratory rate (after sitting for at least 5 minutes).

⁵ Expanded Disability Status Scale should be performed by a study certified rater. Where applicable, refer to study manual for instructions.

⁶ [REDACTED]

⁷ Sites and technicians must be qualified and approved by the central reader to perform [REDACTED], full-field visual evoked potential, and [REDACTED].

[REDACTED]

¹² Adverse event/serious adverse event monitoring will be recorded after informed consent form sign-off through the end-of-study visit.

CONFIDENTIAL

The information contained herein may not be used, disclosed, or published without the written consent of Biogen MA Inc.

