7.4. End of Study

The end of study is last subject, last visit for final collection of data.

CONFIDENTIAL

The information contained herein may not be used, disclosed, or published without the written consent of
Biogen MA Inc.

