### **3.4.2 Clinical Adverse Events**

For this study, any AE experienced by the subject after ICF sign-off through the end-of-study visit is to be recorded on the CRF, regardless of the severity of the event or its relationship to the investigational drug (administered in Study 215ON201) or procedure(s) in this study. Any SAE experienced by the subject between the time the subject has signed the ICF and the End of Study Visit is to be recorded on an SAE Form, regardless of the severity of the event or its relationship to the investigational drug (administered in Study 215ON201) or procedure(s).

All AEs will be coded using the MedDRA. The overall summary table of AEs will present the number of subjects with the following events for each treatment group and overall. A subject is counted only once in each category.

- AE;
- AE with severity as “moderate” or “severe”;
- AE with severity as “severe”;
- investigational drug (administered in Study 215ON201) related AE
- study procedure(s) related AE;
- SAE;
- AE leading to withdrawal from study.

The incidence of AEs will be summarized using the primary system organ class and preferred term. Preferred terms are presented by decreasing incidence in the total column within each system organ class. The incidence of AEs will also be summarized by event severity and by relationship to the investigational drug (administered in Study 215ON201) or study procedure(s) using system organ class and preferred term. Within each system organ class or/and preferred term, the same subject will be counted only once. If a subject

has more than one AE in the same system organ class or/and preferred term, the most severe AE will be reported.

Additionally, the incidence of AEs will be summarized by using preferred term only, and preferred terms will be ordered by decreasing frequency of AEs in the BIIB033 100mg/kg column.

The incidence of SAEs will also be summarized by primary system organ class and preferred term and treatment group as well.

Listings of all AEs, SAEs, and AEs that led to study withdrawal will be presented.

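### Does the medication table need to reach back before consent, to cover MS therapy stopped between the last 215ON201 visit and Day 1?

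*SAP*

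**What the plan says.** SAP 3.2.5 opens the window at consent and closes it at the end of study: "A concomitant medication is any drug or substance administered between the time the subject has signed the ICF and the End of Study". Its output is one table: "The number and percent of subjects taking concomitant medication and non-drug treatments will be summarized by treatment group and overall". SAP Table 1 places consent on Day 1.

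The closing point is worded in more than one way. A footnote to SAP Table 1 says "Completion of the Day 1 visit assessments constitutes the end-of-study visit", and SAP 2.1 gives the visit about one day plus a five-day allowance. The adverse-event section, SAP 3.4.2, uses "between the time the subject has signed the ICF and the End of Study Visit". Protocol 7.4 defines the term for the study as a whole: "The end of study is last subject, last visit for final collection of data".

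The interval since the parent study is covered for medical history but not for drugs. SAP 3.2.4 has "Medical history between last study visit Study 215ON201 and Day 1 is categorized into pre-specified system organ categories", in line with the footnote to the protocol's schedule: "Medical history will be taken from after last study visit in Study 215ON201". The only other readable mention of MS-modifying therapy in the SAP is the per-protocol definition in 3.1, which removes subjects who received it during 215ON201. Protocol version 4.0 (Table 1 and section 11.1) schedules the recording of concomitant therapy and does not say how far back it goes.

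**The concern.** Several secondary outcomes accumulate over the years that the medication window leaves out. Under SAP 3.3.3, time to confirmed MS starts at the diagnosis of optic neuritis. The changes in Gd-enhancing lesions and T2 volume start at the 215ON201 baseline and are compared between arms. Protocol 5.4 describes the available MS drugs as acting on inflammatory activity, which is what those MRI measures are meant to reflect.

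Suppose one original arm had received more MS therapy after the parent study. A difference in lesions or in CDMS could then partly reflect that therapy, and a similar result in both arms could hide a difference. A table limited to a few days around the visit would show current use but not earlier courses or cumulative use. The SAP also treats MS therapy as important enough to define the per-protocol population during 215ON201, and it already looks back to the last parent visit for medical history. Leaving drugs out of that look-back therefore seems an oversight.

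**Working it through.** The plan states no figure to reproduce here, so the check has three parts: the intervals, what the table shows, and what an added table would change.

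**Intervals** (one month = 30.4375 days; 215ON201 baseline taken as Week 0; Week 32 = 32 × 7 = 224 days)

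- Last parent visit to Day 1, for a completer:
  - SAP 1.1, 24 to 28 months: 24 × 30.4375 = 730 days; 28 × 30.4375 = 852 days.
  - Protocol version 4.0 section 6.1, up to 36 months: 36 × 30.4375 = 1,096 days.
- 215ON201 baseline to Day 1: 224 + 730 = 954; 224 + 852 = 1,076; 224 + 1,096 = 1,320 days.
- Share of the MRI interval lying after Week 32 and before consent: 730/954 = 76.5%; 852/1,076 = 79.2%; 1,096/1,320 = 83.0%.
- Medication window if it closes at the subject's own visit: 1 day, or 1 + 5 = 6 days. If it closes at the last subject's last visit it runs on after consent, but nothing before consent is added.

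These shares measure calendar time, not therapy missed. A drug started at any point in that time and still taken at Day 1 is counted.

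**What the table shows**

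| Course of MS-modifying therapy | In the by-arm table of SAP 3.2.5? |
|---|---|
| Started after 215ON201, still in use at Day 1 | Yes, without its start date |
| Started after 215ON201, stopped before consent | No |
| Used only during 215ON201 | No, but the subject is outside the per-protocol set |

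**What an added history table would change**

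- Primary FF-VEP change: the ANCOVA in SAP 3.3.1 has the baseline value and treatment group as its only terms. It would stay the same.
- CDMS: counts, percentages and Kaplan-Meier estimates by arm, with no named test in 3.3.3. These would stay the same.
- EDSS, SDMT and MSFC: descriptive. These would stay the same.
- Gd-enhancing lesions and T2 volume: compared between original arms whatever therapy came later. These would stay the same.
- Analysis populations: the per-protocol rule concerns therapy during 215ON201 only, so membership would stay the same.

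**The case for a change.** The strongest case for a change is transparency at low cost. It needs a sentence in the SAP, a look at the CRF and one or two tables, at a visit where history since the last parent visit is taken anyway. Fixing the look-back in advance would also avoid choosing a therapy window after the results are known. The reading of the text behind this is right: 3.2.5 does exclude therapy that ended before consent, and the interval lengths are correct.

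Much of the rest does not stand.

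- Therapy that began after randomisation may itself be a consequence of treatment or of disease course. Adjusting for it could bias a comparison by original arm, so the table could serve only as background.
- A stricter reading would omit a patient on long-interval dosing who had no dose inside the window. That sits badly with the table's own wording, which counts people taking a drug.
- Corticosteroid courses have no support in the documents as a driver of these outcomes. Protocol 5.4 does not list them, and 5.2 discusses them for acute optic neuritis, with no long-term visual benefit.
- The gap is longer for early withdrawals, by at most 224 days, but they can enter only the ITT sensitivity analyses. The per-protocol set, which the SAP makes primary, is restricted to completers of 215ON201.
- A table starting at the last parent visit would misdate first use for ITT subjects who began therapy during 215ON201, so the obvious remedy has a defect of its own.

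Absence is also not fully established. Parts of the SAP are blacked out, including text around the subgroup list in 3.1, and the CRF is not available.

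**Conclusion.** No change to the plan is needed. Counting drugs from consent to the end of study is a coherent definition that matches the adverse-event window in SAP 3.4.2, and it captures MS therapy in use at Day 1 by original arm. The part left out is therapy stopped before consent, together with the start dates of ongoing therapy. That is a limit on descriptive context for the secondary outcomes. It leaves every planned estimate, test and population as it is, and the primary FF-VEP analysis is untouched.

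The difference between end of study and end-of-study visit is a matter of wording that an analyst will settle from SAP Table 1 and section 3.4.2. If the CRF holds start and stop dates, a descriptive table of MS-modifying therapy can be produced at reporting without amending the SAP. It would best run from the first dose in 215ON201, using parent-study records for that period, and be presented as background only.

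This rests on two assumptions: that the comparisons are meant to be read by original arm regardless of later therapy, and that no blacked-out text makes post-study therapy an adjustment factor. The number of subjects who stopped therapy before consent cannot be obtained from the documents.
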